9.4.2. Corrected QT interval

The QT interval (measured in milliseconds) is the time between the beginning of the Q wave and the end of the T wave in the cardiac cycle. The QT interval represents the process of electrical depolarization and repolarization of the ventricles. The QT interval is affected by heart rate, and a number of methods have been developed to correct the QT interval using heart rate.

The QT (QTc) interval (QTcF), corrected using the Fridericia method, is as follows:

$$QTcF = \frac{QT}{\sqrt[3]{RR}}$$

where QT is measured in milliseconds; RR = 60/heart rate (beats/minute) and RR is measured in seconds.

The maximum post dose change in QTcF interval values obtained during the study will be summarized within the following categories:

- Maximum QTcF≤ 450 ms and change from baseline > 30 ms
- Maximum QTcF≤ 450 ms and change from baseline > 60 ms
- Maximum QTcF> 450 ms and change from baseline > 30 ms
- Maximum QTcF > 450 ms and change from baseline > 60 ms
- Maximum QTcF > 480 ms and change from baseline > 30 ms
- Maximum QTcF > 480 ms and change from baseline > 60 ms
- Maximum QTcF > 500 ms and change from baseline > 30 ms
- Maximum QTcF > 500 ms and change from baseline > 60 ms

The QTcF interval and uncorrected QT interval results and their change relative to baseline at each visit (nominal visit) will be summarized by treatment group, using descriptive statistics. ECG results measured at the unplanned visit before the first dose of medication will be included in the selection of baseline values.

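### SAP 9.4.2 counts QTcF above 450, 480 and 500 ms only together with a change above 30 or 60 ms, so no planned table gives the number of subjects per arm above each cut-off

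*SAP*

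**What the plan says.** SAP 9.4.2 defines QTcF by the Fridericia correction and introduces the categorical table thus: "The maximum post dose change in QTcF interval values obtained during the study will be summarized within the following categories". Eight categories follow. Two apply a ceiling on the maximum, "Maximum QTcF≤ 450 ms and change from baseline > 30 ms" and "Maximum QTcF≤ 450 ms and change from baseline > 60 ms". The other six apply a floor of 450, 480 or 500 ms, each paired once with a change above 30 ms and once with a change above 60 ms. The rows at 450 ms are "Maximum QTcF> 450 ms and change from baseline > 30 ms" and "Maximum QTcF > 450 ms and change from baseline > 60 ms". The highest cut-off begins with "Maximum QTcF > 500 ms and change from baseline > 30 ms".

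The other planned ECG outputs are:

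- descriptive statistics of QTcF, uncorrected QT and their changes by nominal visit (SAP 9.4.2);
- a shift table of the investigator's normal/abnormal assessment, with a by-subject listing (SAP 9.4.1);
- a listing of ECG results (Protocol 8.7.5).

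SAP 9.4 leaves room for further analyses if something of interest appears, but specifies none. Protocol 7.6.3.3 schedules ECGs at screening and EOT, with more as clinically indicated.

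**The concern.** Cut-offs of 450, 480 and 500 ms are useful only if the absolute level matters in its own right. Yet here the level is never counted by itself. A reader who sees a row for values above 500 ms may take it as the number of subjects who exceeded 500 ms, when it is only the number who did so and also rose by more than 30 ms. A subject who starts with a long QTcF needs only a small rise to cross a cut-off, and that is the subject the joint rows leave out. The visible exclusion criteria (Protocol 4.2, partly redacted) set no QTc limit, so such subjects are not visibly kept out of the trial.

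What is at stake is a descriptive safety count per arm. All safety analyses are descriptive (Protocol 8.7), so no test or error rate depends on it.

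**Working it through.** The plan states no figure to reproduce here. The check is of the logic of the categories.

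**Inputs (SAP 9.4.2).** Let M be a subject's maximum post-dose QTcF, B the baseline, and C = M − B the change. B is fixed for each subject, so the largest change occurs at the largest value, and M and C describe the same ECG. The eight rows are:

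| Row | Condition on M (ms) | Condition on C (ms) |
|---|---|---|
| 1 | ≤ 450 | > 30 |
| 2 | ≤ 450 | > 60 |
| 3 | > 450 | > 30 |
| 4 | > 450 | > 60 |
| 5 | > 480 | > 30 |
| 6 | > 480 | > 60 |
| 7 | > 500 | > 30 |
| 8 | > 500 | > 60 |

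**Step 1: who is in no row.** Every row requires C > 30 at least. So any subject with C ≤ 30 is in no row, whatever the value of M.

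| B | M | C = M − B | Rows |
|---|---|---|---|
| 480 | 508 | 28 | none |
| 480 | 510 | 30 | none |
| 479 | 510 | 31 | 3, 5, 7 |
| 449 | 510 | 61 | 3, 4, 5, 6, 7, 8 |
| 465 | 490 | 25 | none |
| 445 | 455 | 10 | none |
| 405 | 440 | 35 | 1 |

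The rows were also run over whole-number pairs with M from 501 to 600 and C from −100 to +30, which is 100 × 131 = 13,100 pairs. None fell in any row.

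**Step 2: which baselines allow it.** If M > T and C ≤ 30, then B = M − C > T − 30. For T = 500 the baseline must exceed 470 ms, for T = 480 it must exceed 450 ms, and for T = 450 it must exceed 420 ms. The documents give no baseline QTcF distribution, so these bounds cannot be turned into a count.

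**Step 3: what can be rebuilt from the table.** Rows 1 and 3 split all subjects with C > 30 by whether M is above 450, and rows 2 and 4 do the same for C > 60. Hence

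- N(C > 30) = row 1 + row 3
- N(C > 60) = row 2 + row 4.

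As a check, all 251 × 120 = 30,120 pairs with M from 350 to 600 and C from 31 to 150 were counted at least once. The change axis has no gap.

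For the absolute level,

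- N(M > 500) = row 7 + N(M > 500 and C ≤ 30),

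and the second term is in no row. The same holds at 480 ms with row 5 and at 450 ms with row 3. The table gives only a lower bound for each absolute count.

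**Step 4: do other summaries supply it?** The by-visit statistics include a maximum (SAP 3.1), but a maximum shows one extreme value and not how many subjects crossed a line. The shift table uses the investigator's judgement, not a QTcF value. Listings allow a hand count but are not a summary by arm.

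**Step 5: comparison within the SAP.** Section 9.2.3 counts AST, ALT, total bilirubin and ALP against stand-alone multiples of the upper limit of normal, and then adds joint rows for AST or ALT with bilirubin. Section 9.4.2 has joint rows only.

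**The case against.** The strongest reply is that the table does what it announces. Its lead-in concerns the maximum change, SAP 9.4 says the ECG analysis is meant to find meaningful changes, and Protocol 8.7.5 asks only that ECG results, including QTc change, be summarized and listed. On that view it is a table of change split by level, and no passage promises a count by level alone. This stands: the SAP does not contradict itself or the protocol, and the point is an addition rather than the correction of an error.

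It is also true that the subject is not hidden. The value is listed. It may appear as the by-visit maximum, and in the shift table if the investigator judged the ECG abnormal. Protocol 7.6.3.3 has clinically significant abnormalities reported as adverse events or medical history. The one visible hERG result (Protocol 1.2.3.2) is a 12.0% inhibition at 225 μM, which the protocol regards as unlikely to matter clinically.

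A reader might infer three stronger things, none of which the documents support:

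- **That the trial will understate QT prolongation.** It can leave subjects out of the categorical count, but nothing shows that any such subject exists, and the table is not presented as a count of prolonged QTcF.
- **That change above 30 or 60 ms is also under-counted.** It is not: those totals are sums of two existing rows.
- **That missing baselines are a further material gap.** Any table of change omits such subjects. A screening ECG is required for all, and unplanned pre-dose ECGs are eligible as baseline (SAP 9.4.2), so there is no reason to expect many.

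What the reply does not answer is that the count per arm above each cut-off is absent from every planned summary, although the SAP itself chose those cut-offs.

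**Conclusion.** The point holds as a gap in descriptive safety reporting. All eight categories require a change above 30 ms, so a subject above 450, 480 or 500 ms with a change of 30 ms or less is in none of them, and the absolute counts cannot be recovered from the table. This follows from the wording of SAP 9.4.2 and assumes only that the change is taken against a single baseline per subject. The size is unknown and may be zero, because it depends on how many subjects enter with a QTcF above 420, 450 or 470 ms (for the three cut-offs in turn) and then cross the line. The primary mortality analysis and its conclusion are not affected. This is a cheap improvement, not an error that threatens the trial.

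**What to change.** Add three rows to the SAP 9.4.2 table: maximum post-dose QTcF above 450 ms, above 480 ms and above 500 ms, each regardless of change from baseline. Keep the eight joint rows. Change-only rows are not needed, because each equals the sum of the ≤ 450 and > 450 rows at that change threshold. The layout then matches SAP 9.2.3, with stand-alone thresholds first and joint criteria after.

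With the added rows, the example of baseline 480 ms and maximum 508 ms goes from no row to three. No new data are needed. The only downside is a slightly longer safety table. If the SAP is already final, its section 1 provides for later changes to be documented in the clinical study report.

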9.5. Physical Examination

A shift table of the physical examination results at each visit (nominal visit) compared with baseline values will be presented by treatment group using the following categories: normal; abnormal, not clinically significant; abnormal, clinically significant; or missing. The number and percentage of subjects in each cross-classification group of the shift table will be presented. Subjects with a missing value at baseline or postbaseline will not be included in the denominator for percentage calculation.

A by-subject listing of physical examination will be provided by visit in chronological order.

10. PHARMACOKINETIC (PK) ANALYSIS

10.1. Pharmacokinetic Sample Collection

XNW4107-302 Blood samples for XNW4107, imipenem, and cilastatin plasma drug concentrations were collected prior to administration on Day 4 (+2 days), 5-25 min and 2-3 hours after completion of the 30-min intravenous infusion on that day. These samples may be collected at the time of any of the 4 infusions on Day 4 (+2 days).

10.2. Pharmacokinetic Analysis

Pharmacokinetic analysis will be summarized based on the pharmacokinetic population.

Concentration time data for XNW4107, imipenem, and cilastatin will be analyzed and summarized using descriptive statistics (number of subjects, arithmetic mean, geometric mean, median, first quartile, third quartile, standard deviation, minimum, maximum, coefficient of variation, and geometric coefficient of variation) for each of the specified sampling time windows.

In the summary statistics, the BLQ values at all time points are considered to be zero.

Concentration-time data at each scheduled collection timepoint will be displayed graphically on the linear and semi-logarithmic scales as mean + standard deviation.

A by-subject listing of PK sampling details will be provided by visit in chronological order.

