3.6. Data Processing and Derivation Rules

The rules regarding PK data are detailed in chapter 10.

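### SAP 10.2 sets BLQ concentrations to zero in all PK summary statistics but also requires the geometric mean and geometric CV, which cannot take a zero

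*SAP*

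**What the plan says.** SAP 10.2 lists the statistics for the XNW4107, imipenem and cilastatin concentrations. The list contains "number of subjects, arithmetic mean, geometric mean, median, first quartile, third quartile, standard deviation" and ends with "coefficient of variation, and geometric coefficient of variation) for each of the specified sampling time windows". The handling rule follows: "In the summary statistics, the BLQ values at all time points are considered to be zero". It names no exception for statistics computed on the log scale.

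The concentration plots are to be "displayed graphically on the linear and semi-logarithmic scales as mean + standard deviation".

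SAP 10.1 gives the sampling scheme: samples "were collected prior to administration on Day 4 (+2 days), 5-25 min and 2-3 hours after completion of the 30-min intravenous infusion".

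No other rule fills the gap. SAP 3.6 states: "The rules regarding PK data are detailed in chapter 10". The substitution for values reported as less than a limit, in SAP 3.6.1, is for safety and efficacy data. Protocol 8.8 lists the geometric mean (not the geometric CV) and has no BLQ rule. The text of Protocol 7.7 is not visible in the public version.

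**The concern.** The geometric mean and geometric CV are computed from logarithms, and zero has no logarithm. The list of statistics and the BLQ rule therefore conflict at the first BLQ value in any window. The SAP does not say which gives way, so the programmer has to decide.

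There are two likely outcomes. One is a table showing a geometric mean of 0 and a blank geometric CV. The other is that the log of zero becomes missing. The geometric statistics then describe only subjects above the limit, while the arithmetic statistics beside them describe everyone. The second is harder to notice, because the numbers look ordinary and nothing in the SAP requires the smaller denominator to be shown. The values lost would be the low exposures. The pre-dose sample is the plausible place for them, and PK evaluation is a stated secondary objective (SAP 1.1.2).

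**Working it through.** The plan gives no figure to reproduce here. The check is of the definitions, followed by an illustration of size.

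**Definitions.** Geometric mean GM = exp(mean of ln x), equivalently (product of x)^(1/n). Geometric CV = 100 × sqrt(exp(variance of ln x) − 1). The plotted quantity is the arithmetic mean, with mean + SD as the upper bar.

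**Step 1: what zeros do.** Assumed data: 100 simulated lognormal values (log-mean 0, log-SD 1, all above 0.1), with the lowest k set to zero.

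| k zeros | GM, literal | Geometric CV, literal | n if zeros dropped | GM, dropped | Geometric CV, dropped | Arithmetic mean | Mean + SD |
|---|---|---|---|---|---|---|---|
| 0 | 0.95 | 97% | 100 | 0.95 | 97% | 1.302 | 2.53 |
| 1 | 0 | undefined | 99 | 0.97 | 93% | 1.301 | 2.53 |
| 5 | 0 | undefined | 95 | 1.04 | 83% | 1.294 | 2.53 |
| 20 | 0 | undefined | 80 | 1.28 | 62% | 1.242 | 2.53 |
| 100 | 0 | undefined | 0 | none | none | 0 | 0 |

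One zero is enough to break both geometric statistics. The arithmetic mean stays positive, and so can be drawn on a log axis, until every value in the window is BLQ.

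**Step 2: size if zeros are dropped.** Assume lognormal concentrations with arithmetic CV c and a fraction q below the limit.

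- σ = sqrt(ln(1 + c²)); z is the q-quantile of the standard normal, φ its density at z, and m = φ/(1 − q).
- GM with BLQ dropped ÷ true GM = exp(σm).
- Log variance after dropping = σ²(1 + zm − m²).
- GM with LLOQ/2 ÷ true GM = exp[q(σz − ln 2) + σφ].

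Worked case, c = 100%, q = 10%: σ = 0.8326, z = −1.2816, φ = 0.1755, m = 0.1950.

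- Dropped: exp(0.8326 × 0.1950) = 1.176, an overstatement of 17.6%.
- Log variance: 0.6931 × 0.712 = 0.494, so the geometric CV is 80% instead of 100%.
- LLOQ/2: exp[0.1 × (−1.0671 − 0.6931) + 0.8326 × 0.1755] = exp(−0.030) = 0.970, an understatement of 3.0%.

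| CV (assumed) | BLQ (assumed) | GM error, dropped | Geometric CV, dropped | GM error, LLOQ/2 |
|---|---|---|---|---|
| 60% | 5% | +6.2% | 53% | −2.3% |
| 60% | 10% | +11.4% | 50% | −4.2% |
| 60% | 20% | +21.4% | 44% | −7.4% |
| 100% | 5% | +9.5% | 87% | −1.7% |
| 100% | 10% | +17.6% | 80% | −3.0% |
| 100% | 20% | +33.8% | 71% | −4.5% |
| 150% | 5% | +12.5% | 126% | −1.2% |
| 150% | 10% | +23.6% | 115% | −1.8% |
| 150% | 20% | +46.2% | 99% | −1.7% |

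**The case against.** The strongest reply is that this may never arise. Samples are taken on Day 4 (+2 days) under 6-hourly dosing, so each pre-dose sample follows repeated doses. No quantification limit, trough concentration or BLQ rate is visible, and a BLQ sentence is routine in a PK section. That stands: a reader might infer from the rule that the sponsor expects BLQ values, but the documents do not show it. If none occurs, there is no effect. It does not rescue the rule, whose only purpose is to cover the case in which one does occur.

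Three stronger readings are tempting and are not supported:

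- **The semi-log plots fail too.** They show the arithmetic mean with an upward SD bar. That mean is positive unless the whole window is BLQ, so they need no change.
- **The plan biases the geometric mean upward.** The SAP does not say that zeros are dropped. Read literally, it yields 0, an error in the opposite direction. The upward bias is conditional on how the software treats the log of zero.
- **Any BLQ value makes the summaries undefined.** The arithmetic mean, SD, median, quartiles, minimum and maximum all accept zeros. The geometric mean is degenerate (0), and only the geometric CV is strictly undefined.

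It is also fair to object that LLOQ/2 is one workable convention among several and has a small bias of its own. That stands too, and it is a reason to state the choice in advance.

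**Conclusion.** The point holds for the geometric mean and geometric CV only. It is more than a missing detail, because following the stated rule with one BLQ value gives a wrong result for one statistic and no result for the other.

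If zeros are dropped instead, the geometric mean is overstated by about 6-13%, 11-24% or 21-46% at 5%, 10% or 20% BLQ, and the geometric CV shrinks. These ranges rest on assumed lognormal concentrations with a CV of 60-150% and on assumed BLQ rates.

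The consequence is limited to descriptive PK tables for the test-drug arm (SAP 3.2.10). No hypothesis test uses them, and the mortality analysis is untouched. A reader might infer that the population PK modelling in SAP 1.1.2 is affected, but nothing in the documents makes these summary tables its input. The rule is wrong as written, with low priority.

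**What to change.** Add to SAP 10.2:

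- Zero is kept for the arithmetic statistics and for the mean + SD plots on both scales.
- For the geometric mean and geometric CV only, BLQ values take a stated positive substitute, such as LLOQ/2.
- The number of BLQ values is shown per analyte and sampling window.
- Geometric statistics are not reported where most values in a window are BLQ.

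The cost is a few lines of text and minor programming, with no new data. There are two downsides. LLOQ/2 leaves a downward bias of about 1-7% in the geometric mean under the assumptions above. The same sample would also carry two values in one table, zero for arithmetic and the substitute for geometric statistics, which needs a footnote.

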11. CHANGES FROM PROTOCOL-SPECIFIED ANALYSIS

Subjects will be randomly assigned to treatment groups in a 1:1 ratio (Protocol V1.0) and a 2:1 ratio (Protocol V3.3 and beyond) using stratified randomization via interactive voice or web-based response systems (IRT). In the final analysis, the data will contain subjects enrolled in both randomized ratios.

In the protocol, for the primary efficacy endpoint, the randomization stratification factor-corrected Mantel-Haenszel stratification method (Koch, 1989) will be used to provide the difference in proportions between groups (i.e., rate difference: IMI-XNW4107 group minus IMI/REL group) and their 95% two-sided CIs. However, due to the number of subjects actually enrolled in other countries and regions outside of China was very small, in Section 8.1.2.1, country/region (China vs. other countries and regions) in the randomization stratification factor was excluded from the analysis, and treatment comparisons were made by the following stratification factor (IMI XNW4107 group minus IMI/REL group):

- Type of infection (non-ventilated HABP vs. ventilated HABP).
- APACHE II scores (<15 versus ≥ 15).

New extended micro-MITT 2 analysis population and addition of microbial efficacy by subject and microbial efficacy by pathogen in the extended micro-MITT 2 population.

For imputation rules of all-cause mortality (except for sensitivity analyses), subjects with unknown survival status at Day 14 and Day 28 will not be considered deaths in either treatment group.

[figure not shown]
[figure not shown]
[figure not shown]
[figure not shown]
[figure not shown]
[figure not shown]
[figure not shown]
[figure not shown]
[figure not shown]
[figure not shown]

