3.4. Stratification Factors and Covariates

Subjects will be randomly assigned to treatment groups in a 1:1 ratio (Protocol V1.0) and a 2:1 ratio (Protocol V3.3 and beyond) using stratified randomization via an interactive voice or web-based response system (IRT). Stratification will be based on the following variables:

- Type of infection (non-ventilated HABP vs. ventilated HABP).
- Acute Physiology and Chronic Health Evaluation II (APACHE II) scores (<15 versus ≥ 15).
- Country/Region (China & Rest of the World).

If there is a difference in the stratification factors between the IRT and the EDC, the value recorded in the EDC will be used in the analysis. In addition, this difference will be presented in the statistical analysis.

For efficacy endpoints, stratification variables will be included as covariates in the efficacy analysis model.

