8.1.2.2. Sensitivity Analysis

In the primary analysis, for both treatment groups, subjects with unknown survival at Day 14 will be considered missing. To evaluate the impact of missing data on all-cause mortality at Day 14, the following multiple fill method will be used:

Considering that within the same treatment group, within the same randomization stratification, subjects with unknown survival at day 14 and subjects with no deletions have similar outcomes, the data from all observed subjects with unknown survival at day 14 will be used to fill in subjects with unknown survival at day 14 in a multiple imputation method. A logistic regression model (logistic regression) will be used to generate the post-fill dataset, and the following covariates will be included in the model: treatment group (test drug vs. control drug), type of infection (non-ventilated HABP vs. ventilated HABP), and APACHE II scores (continuous variable). Newly generated datasets after filling were analyzed using the same methods as

described in Section 8.1.2.1. The results of these analyses were then finally combined using Rubin's Rule (Rubin's Rule) to derive the difference in proportions of the IMI-XNW4107 group minus the IMI/REL group and their two-sided 95% confidence intervals.

For the MITT population, the p-value from the stratified log-rank test comparing the IMI-XNW4107 group and the IMI/REL group will be provided, accompanied by Kaplan-Meier curves; the hazard ratio and its 95% confidence interval between the IMI-XNW4107 group and IMI/REL group will be calculated using a stratified Cox regression model.

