14. SAP VERSION REVISIONS

Revision date	Section	Summary of Revisions	Reason for Revision
June 25, 2025	Department of Biostatistics	
 1. Update abbreviations. 2. Revise descriptions in the Microbiology Data section. 3. For all-cause mortality imputation (excluding sensitivity analyses), Subjects with unknown survival status at Day 14/Day 28 shall not be considered deaths in either treatment group. Survival analysis has been added. 4. Any pathogen detected in blood culture samples is defined as bacteremia. 5. For pathogens missing IMI/REL susceptibility data, impute using IMI susceptibility results. 6. In primary Estimand, APACHE II score is used as a continuous variable in the sensitivity analysis. 	
 1. Added new abbreviations. 2. Added detailed descriptions. 3.  4.  5.  6.  7.  8.  9.  10.  11.  12.  13.  
subjects with missing survival status will not be considered deaths. Results of the survival analysis were also supplemented.
 
4. The definition of bacteremia was updated based on expert judgment.
 
5. The mechanism of action of imipenem/relebactam (IMI/REL) is that relebactam inhibits bacterial β-lactamases, thereby restoring activity against imipenem-resistant pathogens. For pathogens inherently susceptible to imipenem, relebactam is not required. Therefore, for imipenem-susceptible pathogens missing IMI/REL susceptibility data, susceptibility to IMI/REL shall be imputed as susceptible (S).
 
6. All-cause mortality in the trial was low, and some strata at randomization contained no deceased subjects; these data could not be used for imputation.

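### Subjects randomised 1:1 and later 2:1 are pooled without a period stratum, so an unexplained mortality change between the two periods would bias the primary difference

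*SAP*

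**What the plan says.** SAP Section 3.4 records a change of allocation during the trial: "Subjects will be randomly assigned to treatment groups in a 1:1 ratio (Protocol V1.0) and a 2:1 ratio (Protocol V3.3 and beyond". Section 11 repeats this and adds that "In the final analysis, the data will contain subjects enrolled in both randomized ratios".

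The primary analysis (Section 8.1.2.1) is a stratum-weighted Mantel-Haenszel risk difference. Non-inferiority is concluded if the upper two-sided 95% limit is at most 10%. Section 11 drops region because few subjects were enrolled outside China, and says "treatment comparisons were made by the following stratification factor (IMI XNW4107 group minus IMI/REL group", listing two factors: "Type of infection (non-ventilated HABP vs. ventilated HABP" and "APACHE II scores (<15 versus ≥ 15".

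The imputation model in Section 8.1.2.2 lists "treatment group (test drug vs. control drug), type of infection (non-ventilated HABP vs. ventilated HABP), and APACHE II scores (continuous variable". In the same section a log-rank test is called stratified, and the hazard ratio "will be calculated using a stratified Cox regression model"; neither statement names its strata. The subgroup list in Section 8.1.2.4 contains no period, protocol-version or allocation-ratio factor. The sample size text (Section 1.3) and the arm sizes of 300 and 150 (Section 1.2) treat the whole trial as 2:1.

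**The concern.** Randomisation protects the comparison within each allocation period. Once two ratios are pooled, treatment is associated with period, because the 1:1 period always forms a larger fraction of control than of test.

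Two things do no harm here. Drift inside a period does not bias the difference, and case mix captured by infection type and APACHE II is already adjusted. What is left is a mortality change between the two periods that those factors do not explain, such as a change in sites, supportive care or pathogens.

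If unexplained mortality was higher in the 1:1 period, control looks worse and non-inferiority is easier to declare. If it was lower, the test arm looks worse. The trial's claim rests on one confidence limit against a 10-point margin, and the possible bias comes from a design change that the SAP discloses but does not handle.

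**Working it through.** **1. The plan's own figure.** Inputs from SAP Sections 1.2 and 1.3: 10% mortality in both arms, 300 and 150 subjects, margin 10 points, one-sided 0.025.

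- SE = √(0.09/300 + 0.09/150) = 0.030
- Power = Φ(0.10/0.030 − 1.96) = Φ(1.37) = 91.5%

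The stated power of more than 90% is reproduced.

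**2. Share gap.** Let k subjects be randomised 1:1 and 450 − k be randomised 2:1. The documents do not give k, so a range is assumed.

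- Test arm = k/2 + 2(450 − k)/3
- Control arm = k/2 + (450 − k)/3
- Gap = (k/2)/control − (k/2)/test

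For k = 50, test = 25 + 266.7 = 291.7 and control = 25 + 133.3 = 158.3. The early shares are 8.6% and 15.8%, a gap of 7.2 points.

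**3. Bias.** With D the unexplained early-minus-late mortality change, the bias in test minus control is −gap × D.

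| k at 1:1 | Gap (points) | Bias if D = +5 points |
|---|---|---|
| 30 | 4.6 | −0.2 |
| 50 | 7.2 | −0.4 |
| 100 | 12.4 | −0.6 |
| 150 | 15.6 | −0.8 |
| about 218 (maximum) | 17.2 | −0.9 |

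The sign reverses if D is negative.

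**4. Effect on the non-inferiority decision.** The Section 8.1.2.1 interval was simulated with 60,000 runs per scenario, dividing the SE by the sum of the weights. The printed formula lacks that divisor, possibly through text extraction. Further assumptions:

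- Stratum mix 30/20/20/30%.
- Relative risks 0.5/1/1/1.6.
- Period effect independent of stratum.
- True difference exactly 10 points.

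With no period change the interval is slightly conservative, with an error of about 1.9–2.0%.

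| k at 1:1 | Control mortality 13% early, 8% late | 18% early, 8% late |
|---|---|---|
| 30 | 2.2% | 2.6% |
| 50 | 2.4% | 3.2% |
| 100 | 3.1% | 4.5% |
| 150 | 3.5% | 5.6% |

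Repeat runs agree to within about 0.2 points; at k = 50 and 13% vs 8% one gave 2.5%. With period added as a stratum, the error is 1.6–2.0% in all these cases and the bias is within 0.03 points of zero.

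**5. Break-even.** Error passes 2.5% once early mortality exceeds late by about 8–10 points (k = 30), 6 (k = 50), 4 (k = 75), 3 (k = 100) or 2 (k = 150).

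**The case against.** The strongest reply is that the effect depends on two unknowns, the 1:1 count and a mortality shift for which the documents offer no evidence. Even then it is small beside a 10-point margin and an SE of about 3 points. Only one direction of change threatens the conclusion, and the interval is conservative enough to absorb a small one. The 18% vs 8% column is a stress test, since the SAP's revision history says "All-cause mortality in the trial was low, and some strata at randomization contained no deceased subjects". All of this stands, and it limits the severity.

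A second reply is that the SAP has been removing strata because cells are thin, and that period would double four strata to eight. The cost is real, which is why the fix needs a collapsing rule and why a sensitivity analysis is an acceptable minimum.

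Third, Section 3.4 says the stratification variables enter the efficacy models, so the log-rank and Cox strata can be inferred. That is a fair reading. However, Section 8.1.2.2 does not say whether region is kept, and period is absent either way.

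Finally, the protocol's primary-analysis section is redacted and some SAP content is not shown. The absence of a period term is established only for the visible text.

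**Conclusion.** The concern holds. On the visible text, nothing in the primary, imputation, survival or subgroup analyses separates the two allocation periods. A between-period mortality change not explained by infection type and APACHE II would bias the primary difference.

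The bias is bounded at about 0.17 times that change. With a 1:1 cohort of 50 or fewer and a change of 5 points or less, the planned analysis stays at about its nominal error. With 100 or more, a change of about 3 points is enough to exceed it. The error rates rest on assumed values for the 1:1 count, stratum mix, stratum risks and period change. The direction of any bias is unknown. The gap should be closed because doing so is cheap, not because an error has been shown.

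**What to change.** Before unblinding:

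1. Add randomisation period, defined by the allocation ratio in force in the IRT when the subject was randomised, as a stratum in the Section 8.1.2.1 analysis and as a covariate in the Section 8.1.2.2 imputation model. Name it, with the other factors, among the strata of the log-rank and Cox analyses.
2. Fix a collapsing rule, because the standard error divides by n − 1. Within a period, if any arm-by-stratum cell has fewer than 2 subjects, merge the APACHE II categories. If a cell still has fewer than 2, merge infection type. Always keep period.
3. Report enrolment and Day 14 mortality by period and arm.
4. In the same edit, align Section 8.1.2.1, which still refers to the randomisation factors in general, with Section 11, which drops region.

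If the sponsor prefers not to alter the primary analysis, the minimum is to prespecify the period-stratified version as a sensitivity analysis and to report item 3.

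The cost is SAP wording and data already held. With no period effect and 10% mortality, the simulated SE rises from about 3.0 to 3.1–3.2 points. Simulated power falls from about 93% to 91–92%, still above the stated 90%. Across four assumed stratum mixes, the collapsing rule is triggered in 75–96% of runs with 20 subjects at 1:1, 15–71% with 30, 0.2–26% with 50 and under 1% with 100.
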